1 PROTOCOL SUMMARY

1.1 SYNOPSIS

Title:	Anxiety and depression in epilepsy: assessing outcomes using the electronic medical record (EMR)
Study Description:	
This is an observational, randomized study among N=30 individuals with epilepsy and high or borderline anxiety or depression symptoms receiving usual care at the Wake Forest Comprehensive Epilepsy Center. Participants are randomized to one of two outcome assessment methods [EMR-based-interventional method vs. telephone-based-standard method] for collecting quality of life, anxiety and depression outcomes at 3 and 6 months, under usual care management.
 
The primary aim of the study is to assess feasibility of EMR-based outcome assessment by measuring 6-month retention. We hypothesize that the primary endpoint, retention within the EMR-outcome assessment arm (defined completion of the 6 –month outcome assessment instruments via the EMR), will be greater than 60%.
 
This hypothesis will be tested by randomizing 30 patients with borderline or clinically significant anxiety or depression symptoms [Generalized Anxiety Disorder-7 (GAD-7) >7 or Neurological Disorders Depression Inventory-Epilepsy (NDDI-E) >13] to both outcome assessment methods during usual care and assessing 3- and 6-month quality of life, anxiety, and depression outcomes using the allocated outcome assessment method (N=15 in each arm).
 
We will also estimate 6-month change in epilepsy-specific quality of life in the entire study group (N=30) during usual care.

Objectives:	
Primary Objective: To assess whether retention in the EMR-based outcome method arm at 6 months is sufficient in pilot testing to support use of this outcome assessment method in future pragmatic trials of management interventions for anxiety and depression in epilepsy.
 
Secondary Objectives:
 
 - To quantify retention at 3-and 6- months in the study population using a standard pragmatic trial outcome measure (telephone outcome assessment), and at 3 months using the EMR based outcome assessment method - To estimate 6-month change in epilepsy-specific quality of life (QOLIE-10, primary outcome) and depression and anxiety (secondary) at 3 and 6 months during usual care, among the feasibility cohort of individuals with

epilepsy and borderline to high anxiety or depression scores at baseline (GAD-7>7 or NDDI-E>13 at time of screening).

Outcomes:	
Primary Endpoint: --% retention in the EMR outcome arm, defined as the % of participants who complete the 6 month outcome instruments in the EMR
 
Secondary Endpoints: --% retention in the telephone outcome arm, defined as the % of participants who complete the 6 month outcome instruments via telephone
 
Quality of life under usual care: --6 month change in QOLIE-10 (Quality of Life in Epilepsy-10) from baseline --3 month change in QOLIE-10 from baseline
 
Other outcomes of usual care: --change in anxiety (GAD-7) score from baseline to 3 and 6-month outcome assessments --change in depression (NDDI-E) score from baseline to 3- and 6-month outcome assessments

Study Population:	30 adults with epilepsy seen in follow-up at the Wake Forest Comprehensive Epilepsy Center with borderline or clinically significant anxiety and/or depression (GAD-7>7 and/or NDDI-E >13) at baseline
Phase:	N/A: this is not a treatment study
Description of Sites/Facilities Enrolling Participants:	Wake Forest Comprehensive Epilepsy Center, a level IV comprehensive epilepsy center in Winston-Salem, NC with a busy outpatient clinic serving patients primarily from Western North Carolina and adjacent states.
Study Duration:	Up to 3 years
Participant Duration:	6 months

1.2 SCHEMA

Figure 1: Study Overview

[figure not shown]

Table 1: Enrollment Criteria

Age \geq 18 years

Completed electronic questionnaires independently in clinic

Borderline or high anxiety and/or depression symptoms

[figure not shown]
GAD-7 $>$ 7

NDDI-E $>$ 13

Epilepsy diagnosis (clinician impression or EEG-based)

NO passive suicidal ideation (NDDI-E item 4 score NOT 3 or 4)

Figure 2: Measures

1.3 SCHEDULE OF ACTIVITIES (SOA)

	Screening Clinic Visit	Post-visit screening	Consent/ Enrollment/ Randomization	3 month outcome assessment	6 month outcome assessment
Procedures*					
NDDI-E	X			X	X
GAD-7	X			X	X
QOLIE-10	X			X	X
EMR question to patient: interest in research?	X				
Eligibility verification: medical chart		X			
Telephone consent			X		
Collect additional brief psychiatric history			X		
Randomize			X		
EMR baseline: demographics			X		
EMR baseline: medications			X		
Management plan from screening usual care visit			X		
Health utilization outcomes				X	X
Feasibility assessments	X			X	X

Key for Schedule of Activities:

*: procedures with **green X** above are administered as part of routine clinical care

2 INTRODUCTION

2.1 STUDY RATIONALE

Anxiety and depression are highly prevalent and major contributors to poor quality of life and other poor outcomes in epilepsy, including increased mortality, health care cost, cognitive dysfunction, medication adverse effects, and poor seizure outcomes¹⁻⁷. Despite this importance, **anxiety and depression are under-recognized and undertreated in epilepsy**, and a recent survey indicated top barriers to addressing anxiety and depression in epilepsy were poor access to psychiatrists and other mental health providers⁸⁻¹⁰. Due to poor access to mental health, solutions such as colocation of psychiatrists and psychologist-driven internet behavioral approaches are not feasible for most epilepsy or neurology clinics⁸⁻¹². In response, neurologist-driven solutions are proposed, including a new epilepsy quality measure for conducting validated anxiety and depression screeners at every neurology visit and many expert publications encouraging direct medication treatment by neurologists^{10; 13-17}. However, significant barriers to screening exist, as >50% of surveyed epileptologists indicated inadequate time to administer screeners¹⁰. In implementing validated anxiety and depression screening during our ongoing learning health system trial, we demonstrated *substantial staffing effort is needed to administer screeners and document in the medical record*. There is also a paucity of data on outcomes of screening and/or treatment of anxiety and depression in epilepsy populations, especially real-world epilepsy clinic populations. Despite conceptions that most epilepsy patients are not receiving treatment for anxiety or depression^{10; 14} our preliminary data indicates *nearly half of those with active anxiety or depression symptoms are on medication treatment, and thus have inadequate symptom relief despite treatment*.

Considering these challenges, streamlined methods of screening and longitudinal outcome assessment are fundamental to assessing outcomes of standard treatment and developing effective pragmatic interventions for anxiety and depression in epilepsy. We propose to **implement and assess a learning health system, electronic medical record (EMR)-based screening and outcome assessment for anxiety and depression in the epilepsy clinic**.

2.2 BACKGROUND

Anxiety and depression in epilepsy are highly prevalent and major independent predictors of poor quality of life. Depression and anxiety occur in up to 40-55% of tertiary care epilepsy patients¹⁸⁻²⁰, and without structured assessment, anxiety is under-recognized¹. Although depression and anxiety are more important predictors of poor quality of life than seizure frequency^{2; 21; 22}, *these symptoms are underdiagnosed and undertreated in epilepsy*^{23; 24}. Treatment of depression and anxiety in epilepsy is important to prevent suicide²⁵ which contributes to excess mortality³, as a potential way to reduce excessive health care use^{4; 26}, and to improve quality of life^{2; 22}. However, **a substantial unmet mental health care need exists in epilepsy**^{8; 9}.

The 2014 American Academy of Neurology Epilepsy Quality Measurement Set introduced a measure to screen for “psychiatric or behavioral health disorders” at each visit, and well-validated, free and brief anxiety and depression screeners exist for epilepsy (the GAD-7 and NDDI-E)²⁷⁻³³. Despite this, my 2016 survey of leading epileptologists indicated few used validated anxiety and depression screening instruments (<9% and <19%, respectively), due to

poor availability of mental health providers and lack of time to administer validated screeners¹⁰. Since then, a newly published Epilepsy Quality Measure (2017 Measure) **requires using validated screeners for anxiety and depression at every visit**¹³. Our experience with an ongoing learning health system pilot trial of neurologist treatment for anxiety and depression has demonstrated extraordinary manpower efforts are required to accomplish screening in an entire epilepsy practice (up to 80-90% effort split among different staff). This validates concern about time-related barriers to administering screeners raised in the 2016 epileptologist survey¹⁰ and **indicates need to develop efficient methods to conduct screening in ways that minimize clinical or research staff time**. Patient entry of questionnaires directly into the medical record via patient portal interfaces, with responses stored as discrete data fields that can then be exported for data analyses are a potential timesaving technique to conduct outcomes research and achieve clinical quality metrics simultaneously. Through the existing multicenter AHRQ-funded collaboration, the Neurology Practice Based Research Network (NBPRN), we currently utilize EMR-based entry of validated anxiety, depression, and epilepsy-specific quality of life measures as discrete data fields^{34; 35}. We also now have access to patient-entered versions of these instruments (Generalized Anxiety Disorder-7, GAD-7, Neurological Disorders Depression Inventory for Epilepsy, NDDI-E, and Quality of Life in Epilepsy-10, QOLIE-10). **Thus, we are uniquely poised to test feasibility of these novel tools for conducting EMR-based outcomes research.**

Identifying effective interventions for mental health comorbidities and testing treatment outcomes are **epilepsy research priorities recognized by the Institute of Medicine, and the National Institute of Neurological Disorders and Stroke (NINDS) epilepsy benchmarks include limiting adverse effects on quality of life for people with epilepsy, including mental health**^{36; 37}. Approaches to treating anxiety and depression in epilepsy (e.g. colocation of a psychiatrist in an epilepsy clinic or internet based cognitive behavioral therapy) may have some impact, but their generalizability is limited due to scarcity of and lack of funding for mental health providers¹⁰⁻¹². Based upon an assumption that medications effective for anxiety and depression in the general population are also effective among people with epilepsy (selective serotonin reuptake inhibitors, SSRI and serotonin and norepinephrine reuptake inhibitors, SNRI), expert publications frequently suggest neurologist treatment of anxiety and depression, and many epileptologists report willingness to prescribe a medication for depression or anxiety^{10; 15; 16}. **However, there is a paucity of data on longitudinal outcomes of anxiety or depression treatment in epilepsy** (whether under experimental treatment conditions or usual care) **and a total lack of longitudinal data on those with potentially clinically significant borderline symptom scores (GAD-7: 7-9, NDDI-E: 14-15)**^{29; 31}. Our preliminary data raise questions regarding whether SSRI/SNRI medications are effective to relieve symptoms of anxiety and depression in epilepsy, as 47% of 106 epilepsy clinic patients with high anxiety or depression scores (GAD-7 \geq 10, NDDI-E $>$ 15) were already treated with an SSRI or SNRI (compared to 24% of all consecutive patients examined in a prior analysis). Our data also raise concern that many patients may be too sick from a psychiatric perspective to be managed by a neurologist, as 28% of 106 with high anxiety or depression scores had a prior psychiatric hospitalization. **Thus, further research to assess longitudinal outcomes of anxiety and depression under usual care circumstances is essential for designing appropriate pragmatic interventions to test in future trials.**

In this study, we aim to introduce a standard care screening and outcome assessment paradigm for anxiety and depression in epilepsy using EMR-based direct patient reported measures to overcome high staffing burden of screening, to assess the feasibility of obtaining

EMR-based research outcome measures, and to generate preliminary longitudinal quality of life outcome data in the setting of usual care.

2.3 RISK/BENEFIT ASSESSMENT

2.3.1 KNOWN POTENTIAL RISKS

This is not a treatment study and the risks associated with study participation are minimal. The anxiety and depression instruments used for eligibility screening are already administered as standard care in our epilepsy center. The current epilepsy quality measurement set includes using standardized instruments to screen for anxiety and depression at each visit, and assessing quality of life at each visit¹³.

Outcome assessments administered during the trial pose minimal if any risk to participants (use of time to complete assessments is the main impact on participants). Completing questionnaires about anxiety or depression may result in awareness of emotional symptoms that participants may not have otherwise recognized.

There is a slight chance that suicidality may be identified during outcome assessment due to the underlying anxiety or depression condition we aim to study. We have outlined robust safety measures used in prior studies by the investigator team, which go beyond institutional clinical protocols for response to these symptoms and thus provide additional safety measures beyond what is typical in standard care. We also anticipate that this would be a rare occurrence, especially because our design excludes individuals with possible passive suicidal ideation at the time of initial screening.

Potential breach of confidentiality is an additional risk; we have outlined methods to minimize this risk in section 10.

2.3.2 KNOWN POTENTIAL BENEFITS

As this is not a treatment study, there is no expected benefit for the participants. The study is expected to yield generalizable knowledge to support future research to improve quality of life in epilepsy.

2.3.3 ASSESSMENT OF POTENTIAL RISKS AND BENEFITS

As described above, there is minimal risk and no expected benefit to individual participants.

3 OBJECTIVES AND ENDPOINTS

OBJECTIVES	ENDPOINTS	JUSTIFICATION FOR ENDPOINTS

Primary
 
To assess whether retention in the EMR-based outcome method arm at 6 months is sufficient in pilot testing to support use of this outcome assessment method in future pragmatic trials of management interventions for anxiety and depression in epilepsy.
	
-% retention in the EMR outcome arm, defined as the % of participants who complete the 6 month outcome instruments in the EMR
	
-obtain realistic estimate of feasibility of long-term EMR-based outcome assessment in this population

OBJECTIVES	ENDPOINTS	JUSTIFICATION FOR ENDPOINTS
Secondary		
To quantify retention at 3-and 6-months in the study population using a standard pragmatic trial outcome measure (telephone outcome assessment), and at 3 months using the EMR based outcome assessment method.	
-% retention at 6 months in the telephone outcome arm, defined as the % of participants who complete the 6 month outcome instruments via telephone
 
-% retention at 3 months in the EMR outcome arm, defined as the % of participants who complete the 6 month outcome instruments via telephone
 
-% retention at 3 months in the telephone outcome arm, defined as the % of participants who complete the 6 month outcome instruments via telephone
	
-to estimate future retention & develop retention strategy
 
-to assist in determining whether future studies should include telephone-or EMR-based outcome assessment for shorter and longer outcome assessment durations

To estimate 6-month change in epilepsy-specific quality of life (QOLIE-10, primary outcome) and depression and anxiety (secondary) at 3 and 6 months during usual care, among the feasibility cohort of individuals with epilepsy and borderline to high anxiety or depression scores at baseline.	
--6 month change in QOLIE-10 from baseline
 
--3 month change in QOLIE-10 from baseline
 
--change in anxiety (GAD-7) score from baseline to 3 and 6-month outcome assessments
 
--change in depression (NDDI-E) score from baseline to 3- and 6-month outcome assessments
	
-to generate preliminary estimates of effect for change in quality of life (and anxiety and depression) at 3- and 6-months from baseline during usual care, inputs that will be important for future trial planning with likely usual care control group

Tertiary/Exploratory		
To explore health utilization outcomes among individuals with epilepsy and high or borderline anxiety and/or depression symptoms at baseline.	
-hospitalizations from baseline to 6 month follow-up
 
-Emergency visits from baseline to 6 months follow up
	
-explore associations between longitudinal anxiety and depression symptom outcomes and health utilization

To assess implementation of point-of care electronic medical record based screening in the epilepsy clinic.	-RE-AIM framework measures	-to explore implementation metrics for the clinical screening protocol

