- Multiple reminders and communications will be utilized to enhance participation in the outcome assessments. Telephone calls will be scheduled at the time of enrollment if possible. The outcome instruments will be mailed to telephone arm participants 10 days before scheduled outcome calls, and they will be sent electronically 10 days prior to target completion date for EMR-arm participants. Two telephone reminders for telephone arm participants, and two electronic reminders for EMR-arm participants will be provided prior to scheduled outcome assessment. Up to 5 attempts to call participants in the telephone outcome assessment arm will be made on separate days, starting at the originally scheduled outcome assessment time. Up to 5 electronic reminders with survey instructions will be sent via the EMR to the EMR arm participants, starting with target date for EMR outcome completion.
- After criteria for retention outcome at 6 months is met (5 reminders after due date for outcome assessment as described above), to reduce potential missing data for the secondary outcomes of 6-month change in quality of life, anxiety and depression, the following will be done. For any EMR-arm participants without successful 6-month outcome collection, 3 attempts will be made to collect outcomes via telephone. For any telephone arm participants without successful 6-month outcome collection, 3 attempts will be made to collect outcomes via EMR.
- Subjects will receive incentive of \$15 gift card for completing the brief baseline telephone interview and \$15 for completing each of the two outcome assessments (3 and 6 months).
- Efforts will be made to recruit any eligible participant seen in the practice, including women and under-represented populations

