8 STUDY ASSESSMENTS AND PROCEDURES

8.1 EFFICACY ASSESSMENTS

Screening Assessment

-NDDI-E, GAD-7, QOLIE-10³⁸

Implementation Monitoring:

RE-AIM framework measures

Feasibility assessments:

Enrollment/Baseline Assessments:

-accrual assessment

Retention: defined as outcomes collected via randomized modality within 1 week of the final of 5 scheduled reminders following outcome assessment due date (see recruitment and retention section for details of reminder process for each arm).

-6 month retention in EMR outcome arm

-6 month retention in the telephone outcome arm

-3 month retention in EMR and telephone outcome arms, respectively

Other feasibility assessments:

-# attempts to contact participants in each arm

-staff time for telephone outcome assessment/telephone contact attempts/preparing mailed survey packets vs staff time to send EMR surveys and electronic reminders

-time for participant completion of EMR surveys

-delay from survey delivery to completion by participant

Usual care outcome assessments (3 and 6 months):

- QOLIE-10
- NDDI-E
- GAD-7
- healthcare utilization (ED visits, hospitalizations)

Review of Clinical Chart: this will be done for preliminary eligibility assessment and for supplementary information on medications prescribed and health care utilization during the study period.

Health Insurance Portability and Accountability Act (HIPAA) rules, other relevant federal or state laws, and local institutional requirements will be followed, as applicable.

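### Section 3 defines 3-month retention in both arms as completing the 6-month instruments by telephone, contradicting its own objective and Section 8.1

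*Combined protocol and SAP*

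**What the plan says.** The secondary part of the Section 3 table has one row on retention. Its objective covers telephone retention at 3 and 6 months "and at 3 months using the EMR based outcome assessment method". Three endpoints follow: telephone at 6 months, EMR at 3 months and telephone at 3 months. The line for EMR at 3 months is "retention at 3 months in the EMR outcome arm, defined as the % of participants who complete the 6 month outcome instruments via telephone". The line for telephone at 3 months differs from it only in naming the other arm: "retention at 3 months in the telephone outcome arm, defined as the % of participants who complete the 6 month outcome instruments via telephone".

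The 6-month telephone endpoint carries the same definition, which is correct for that endpoint. Part of the row's stated justification is "to assist in determining whether future studies should include telephone-or EMR-based outcome assessment for shorter and longer outcome assessment durations".

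Section 8.1 defines retention once, for every time point and both arms, as "outcomes collected via randomized modality within 1 week of the final of 5 scheduled reminders following outcome assessment due date". Among the quantities to be assessed it lists "3 month retention in EMR and telephone outcome arms, respectively".

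The synopsis (Section 1.1) states the 3-month objective correctly, but its endpoint list contains no 3-month retention. Its secondary retention endpoint is the 6-month one: "retention in the telephone outcome arm, defined as the % of participants who complete the 6 month outcome instruments via telephone". Section 9.4.3, on the secondary endpoints, deals with quality of life, anxiety and depression and does not mention retention.

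**The concern.** Retention is the subject of this pilot, and two of its three secondary retention endpoints carry a definition that belongs to a different endpoint. Section 3 and Section 8.1 are the only places that define 3-month retention, and they disagree. An analyst or reader who takes the endpoint table as the formal source would compute or report the wrong quantity.

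The row is meant to inform the choice between telephone and EMR collection over shorter as well as longer follow-up. On the Section 3 wording it gives no information about the shorter period in either arm.

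**Working it through.** **What each line says against what it should measure**

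| Endpoint label (Section 3) | Time point in definition | Method in definition | Required by the objective and Section 8.1 |
|---|---|---|---|
| Telephone, 6 months | 6 months | telephone | 6 months, telephone: agrees |
| EMR, 3 months | 6 months | telephone | 3 months, EMR: both elements wrong |
| Telephone, 3 months | 6 months | telephone | 3 months, telephone: time point wrong |

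The primary endpoint in the same table correctly specifies 6 months and completion in the EMR. The three secondary lines are complete sentences with no gap or redaction. The amendment history records no change to them, so this is current text.

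**Literal value of the 3-month telephone endpoint.** Its definition is word for word that of the 6-month telephone endpoint, so the two values are equal whatever happens at 3 months.

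**Literal value of the 3-month EMR endpoint.** It would count EMR-arm participants who completed the 6-month instruments by telephone. The plan's route to such a completion is the fallback in Section 5.4: "For any EMR-arm participants without successful 6-month outcome collection, 3 attempts will be made to collect outcomes via telephone". Participants retained by EMR at 6 months are not called, so only the others can be counted.

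Inputs:
- n = 15 in the EMR arm (Section 9.2), assuming exactly 15 are analysed.
- r = number retained by EMR at 6 months.
- s = number of the remaining n − r who then complete by telephone. The documents give no success rate, so s can be anything from 0 to n − r.

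Literal value = s/n, with 0 ≤ s/n ≤ (15 − r)/15.

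| r | Lower bound | Upper bound |
|---|---|---|
| 9 | 0% | 6/15 = 40.0% |
| 10 | 0% | 5/15 = 33.3% |
| 11 (Section 9.2 threshold) | 0% | 4/15 = 26.7% |
| 12 | 0% | 3/15 = 20.0% |
| 13 | 0% | 2/15 = 13.3% |
| 14 | 0% | 1/15 = 6.7% |
| 15 | 0% | 0/15 = 0% |

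These are bounds, not forecasts. The upper limit falls as 6-month EMR retention rises. If all 15 completed both assessments in the EMR, Section 8.1 would give 15/15 = 100% at 3 months and the Section 3 wording 0/15 = 0%.

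**The plan's own figure, to confirm that the primary rule is untouched.** Section 9.2 states at least 83% confidence that retention exceeds 0.6 when 11 of 15 are retained. The prior is not stated. With a uniform Beta(1, 1) prior, the posterior is Beta(1 + 11, 1 + 4) = Beta(12, 5), and Pr(p > 0.6) = 0.833, which reproduces the figure. At 10 of 15 it is 0.671, below the required 0.8, so the cut-off of 11 holds. Neither calculation uses the 3-month endpoints.

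**The case against.** The strongest reply is that this is an obvious slip nobody would follow. The endpoint labels name the right arm and the right time. The objective is right in Section 3 and again in the synopsis. The schedule in Section 1.3 places feasibility assessments at both 3 and 6 months, and Section 8.1 supplies a workable definition. On that view the percentage ranges describe a calculation no analyst would make, and the matter is editorial. The absence of retention from Section 9.4.3 also matters little, because Section 9.4.1 already says categorical data will be shown as percentages.

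Much of this stands. The intent is recoverable, a simple proportion needs no further analysis plan, and only two lines are wrong, since the 6-month telephone line has no reason to use 3-month data. The bounds also depend on a denominator of 15. Section 7.1 allows withdrawn randomized participants to be replaced yet still included, so the number analysed could be larger. The bound is then (n − r)/n, and the argument is otherwise the same.

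What does not stand is the step from recoverable intent to leaving the text alone. Section 3 is the formal statement of the endpoints. As written it conflicts with Section 8.1, and neither section says which governs.

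**Conclusion.** The concern holds. Both 3-month retention endpoints in Section 3 are misdefined: the EMR one on time point and method, the telephone one on time point. Read literally, the telephone endpoint repeats its 6-month counterpart. The EMR endpoint is confined to 0 to (15 − r)/15, at most 26.7% at the 11-of-15 threshold, whatever happened at 3 months. Those limits assume 15 analysed and no telephone completion in the EMR arm outside the Section 5.4 fallback.

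The effect is limited to two secondary descriptive endpoints. The primary endpoint, the sample size and the decision rule do not change. No data are lost, because Section 1.3 schedules all three instruments at 3 months for every participant. It should be corrected, but it does not threaten the study's main conclusion.

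**What to change.** Replace the two definitions in Section 3 with wording that follows Section 8.1:

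- *3-month retention, EMR arm: the percentage of participants randomized to EMR who complete the 3-month instruments in the EMR within the Section 8.1 window.*
- *3-month retention, telephone arm: the percentage of participants randomized to telephone who complete the 3-month instruments by telephone within the Section 8.1 window.*

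The primary and 6-month telephone definitions in the table do not mention that window either. One sentence under the table, stating that all four retention endpoints use the Section 8.1 definition, would keep them consistent. Adding the two 3-month endpoints to the synopsis list is optional but would match its stated objective.

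The cost is two corrected lines, plus the cross-reference and two synopsis lines if wanted. Data collection, operations and sample size are unchanged.
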